### **Endpoints:**

Primary endpoint: Device associated thrombus (DAT) at 1-year follow-up imaging by either transesophageal echocardiogram or CT angiography depending on the patient tolerance for TEE (TEE preferred).

Secondary endpoints: Includes ischemic stroke, peripheral thrombo-embolic events, major bleeding requiring intervention (blood transfusion, or surgical or non-operative intervention, i.e., pericardial effusion, vascular access repair etc.).

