Several retrospective studies were published in 2017 supporting the use of NOAC (novel oral anti-coagulant) or DOAC (direct oral anti-coagulant) for anti-coagulation post LAA device implant to reduce DAT. EWOLUTION reported a 1 year device associated thrombus rate of 3.7% with Watchman, independent of the post implant regimen, in which 73% of anti-coagulation 'contra-indicated' subjects were on anti-platelet regimens alone [2]. A separate study showed a 3.2% DAT rate with the Amplatzer Cardiac Plug (previous generation of the Amulet device under IDE trial in the US) [7]. While certainly not what the implanting physician hopes to see at the 45 days or 1 year follow up TEE, whether a DAT leads to clinical ischemic strokes as a whole has been difficult to determine. Standard practice has been to initiate short-term oral anti-coagulation and repeat the TEE in 6 weeks to ensure resolution, of a DAT, then return to anti-platelet therapy alone.

The process of complete endothelialization of a Watchman LAA closure device is poorly understood. Animal models suggest complete endothelialization may be complete within 6 weeks. Human autopsy examples show variable endothelialization at up to 9 months. A study in 2017 using CT angiography demonstrated contrast flow across 66% of LAA devices at 6 weeks, questioning if TEE at 6 weeks is really a suitable metric for 'closure' [8]. Likely this represents a slow leak through the fabric cap and not around the device, if the TEE shows no Doppler flow. We have seen several cases where follow up TEE missed a leak and an obvious gap with contrast filling a trabeculated LAA lobe was seen with CTA. Anti-coagulation was discontinued, but long-term studies are needed to evaluate the impact of this finding.

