## **2. Study design:**

Single arm, prospective unblinded study on post Watchman LAA closure device implant anti-coagulation management at a primary center (Vanderbilt Medical Center) and up to 5 additional high volume LAA implant centers. This trial will be designed to evaluate the use of dabigatran for 90 days post implantation of an LAA closure device (Watchman LAA Closure Device, Boston Scientific Inc.). The drug will be initiated on the morning following device implantation, taken BID per package insert dosing and until follow-up 90-day post implant TEE. Aspirin monotherapy will be utilized in conjunction at 81 mg for up to 12 months, after which the patients will be exited from the study and further treatment decisions will be made by the following physician (see Schedule of Study Procedures at end of protocol). The objective of this trial is to evaluate safety and efficacy of a 90-day period of dabigatran etexilate following LAA closure to prevent device associated thrombus, while minimizing adverse bleeding by eliminating the need for clopidogrel. This is a single arm pilot study with the option (pending collaboration with additional funding source) to expand to a full single arm non-inferiority trial design with 80% power to detect a 1.4% difference with the non-inferiority margin 1% in absolute rate of DAT (control rate 3.9%).

Prospective, non-randomized single arm study. Comparison will be made to historical controls based on published one year DAT rates from PROTECT-AF, PREVAIL clinical trials, and EWOLUTION, and ACP/Amulet registries.

Echocardiography (TEE) will be performed at 90 days (3 months, +/- 2-week window), and again at 1-year post implant (+/- 4 weeks). Selected images will be interpreted by echo lab at coordinating center in an anonymous fashion (patient data de-identified). Ideal imaging will incorporate 0, 45, 90 and 135 degree angled views on the device at follow up.

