Dosing regimen of dabigatran will be by FDA and pharmacokinetic labeling for dabigatran 150mg BID dosing if Creatinine clearance >30mL/min, and 75mg BID dosing if 15-30mL/min. This will be based on calculated CC by baseline labs performed on day of implant. Additional dosing adjustments per package insert for patients taking dronedarone 400mg BID, or ketoconazole will be made consistent with drug label. The majority of subjects will be expected to be on 150 mg BID for 90 days. Subjects on 75 mg twice daily dosing may be enrolled if renal function is stable in the range of 15-30mL/min. Aspirin 81 mg a day will be taken along with oral anticoagulation for 90 days followed by longer-term aspirin 81 mg daily aspirin dose. At the 90 days TEE follow up (3 months) a PCV or CBC will be drawn and compared to baseline PCV pre-LAA closure implant as an assessment of

indolent blood loss (there is expected intra-procedural blood loss from back bleed on access sheaths estimated 25-125mL).

Drug required for study: Initially start with 100 subject pilot study on therapy for 90 days, with option to expand to full non-inferiority study if collaborative funding is secured (IF study expands beyond pilot, estimate 262 subjects, 90 days on therapy). Estimate 80% or more subjects on 150mg BID dosing, and up to 20% subjects on 75mg BID dosing. With either the 100-subject pilot study, or optional expanded single arm study (262 patients) the objective is to establish a device associated thrombus (DAT) rate at 3 months and 1 year within 1.5% or less deviation from published DAT rates at 3.9% (Saw, J., et al). Comparison will be made to published data on Watchman LAA closure utilizing the 45-day warfarin after implant followed by six-month dual antiplatelet regimen, or registry data from European experience on Watchman and Amulet/ACP LAA closure systems.

Patients can be consented for the trial on the day of implantation or up to one month prior in clinic during consultation for LAA closure. This is an unblinded, single arm prospective study. Study exit visit will be coordinated with final twelve-month follow-up imaging after LAA closure implantation.

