### **Statistical Methods/Calculations:**

Statistical sample size calculation to establish comparable DAT rate with the prescribed regimen:

Available data for background on DAT;

Overall incidence of DAT was 3.9% (82 DAT for 2118 implanted devices)

Lempereur et al. Meta-Analysis [ref 19]: 30 studies describing DAT events were included in the analysis. The overall incidence of DAT was 3.9% (82 DAT for 2118 implanted devices). The median time from procedure to diagnosis of DAT was 1.5 months (IQR: 0-2.9). Most cases were diagnosed with transesophageal echocardiogram (TEE). The treatment consisted of low molecular weight heparin (LMWH) in 45.5% of cases, and oral anticoagulation (OAC) or other treatment modalities in 54.5%. Complete thrombus resolution was achieved in 95.0% of cases (100% with LMWH and 89.5% with OAC). Treatment duration varied greatly with a median treatment duration of 45 days (IQR: 14-

135). Clinical events related to DAT consisted of neurologic events namely two transient ischemic attacks (2.4%) and four ischemic strokes (4.9%).

Saw et al [ref 7]. 339 analyzable TEE in follow up. Patients' mean age was  $74.4 \pm 7.5$  years, and 67.3% were men. The mean CHADS2 score was  $2.7 \pm 1.3$ , the mean CHA2DS2-VASc score was  $4.3 \pm 1.5$ , and the mean HAS-BLED score was  $3.0 \pm 1.2$ . Peri-procedural major adverse events occurred in 2.4%. Median clinical follow-up duration was 355 days (range 179 to 622 days). Follow-up transesophageal echocardiography was performed after a median of 134 days (range 88 to 227 days). Device-associated thrombus was observed in 3.2% Independent predictors of device-associated thrombus were smoking (odds ratio: 5.79;  $p = 0.017$ ) and female sex (odds ratio: 4.22;  $p = 0.027$ ).

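### The primary endpoint counts thrombus at the 1-year image, but the 3.9% benchmark is an overall incidence that includes thrombi found early and cleared

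*Combined protocol and SAP*

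**What the plan says.** - **Endpoint.** The Endpoints section reads "Primary endpoint: Device associated thrombus (DAT) at 1-year follow-up imaging", by TEE or CT angiography. The listed secondary endpoints include neither DAT at 90 days nor DAT at any time. The hypothesis in section 1 likewise speaks of DAT rates at 1-year follow-up.
- **Objective.** In section 3, after the exclusion criteria: "the objective is to establish a device associated thrombus (DAT) rate at 3 months and 1 year", compared with a published 3.9%.
- **Benchmark.** Statistical Methods/Calculations takes 3.9% from a meta-analysis of 30 studies: "The overall incidence of DAT was 3.9% (82 DAT for 2118 implanted devices"). On timing: "The median time from procedure to diagnosis of DAT was 1.5 months (IQR: 0-2.9"). On outcome: "Complete thrombus resolution was achieved in 95.0% of cases (100% with LMWH and 89.5% with OAC").
- **Other comparators.** Section 2 promises "historical controls based on published one year DAT rates". Section 1 says "EWOLUTION reported a 1 year device associated thrombus rate of 3.7% with Watchman". Neither says whether the rate is at or through 1 year. For the Amplatzer Cardiac Plug study (3.2%), "Follow-up transesophageal echocardiography was performed after a median of 134 days (range 88 to 227 days").
- **Handling of an early thrombus.** Section 2 allows anticoagulation to be extended and TEE repeated after a 90-day thrombus, at the investigator's discretion. No section says whether a thrombus that then clears is a primary event.

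**The concern.** Three different quantities serve one comparison: a prevalence at one late image, a rate at two time points, and an overall incidence with no stated horizon. A subject with thrombus at 90 days and a clean 1-year image is an event on one reading and a non-event on another, so one dataset gives two primary results. The study is unblinded and single-arm, so the choice could be made with the data in view. The thrombi that the literal wording leaves out are of a kind that the benchmark includes. The stated power is affected as well, because the plan does not say whether the rate assumed for the new regimen is a 1-year or a cumulative rate.

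**Working it through.** **Reproducing the plan's figures.** From Statistical Methods/Calculations: control rate 3.9%, margin 1%, difference 1.4%, level 0.05. The implied true rate is 3.9% - 1.4% = 2.5%, the bound is 3.9% + 1% = 4.9%, and the distance between them is 2.4 points. One-sided normal approximation with the variance at 2.5%:

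- n = (1.645 + 0.842)² × 0.025 × 0.975 / 0.024² = 261.6, so 262.
- Power at n = 100: Φ(√100 × 0.024 / √(0.025 × 0.975) - 1.645) = 45.7%, the stated 46%.

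The arithmetic is sound. What is undefined is the kind of rate that it refers to.

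**Effect of the literal endpoint.** Assumptions:

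- The true cumulative DAT rate is 4.9%, exactly at the bound.
- A share f of DAT is found at the 90-day TEE, and all of it is treated.
- A share s of that clears, with s = 0.895 or 0.95 (the meta-analysis figures for oral anticoagulation and overall), and none recurs.
- The decision rule is an exact one-sided 5% binomial test against 4.9%. The plan names no test.

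The exact rule allows at most 6 events in 262 (P = 0.026; 7 events would give 0.054) and at most 1 in 100 (P = 0.040; 2 would give 0.127).

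Rate at the 1-year image = 4.9% × (1 - f × s).

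| f | 1-year rate | Pass chance, n = 262 (optional) | Pass chance, n = 100 (committed) |
|---|---|---|---|
| every DAT counts | 4.9% | 2.6% | 4% |
| 0.10 | 4.4-4.5% | 5% | 6% |
| 0.25 | 3.7-3.8% | 13-14% | 10-11% |
| 0.50 | 2.6-2.7% | 43-49% | 24-27% |
| 0.75 | 1.4-1.6% | 87-92% | 52-59% |

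The documents do not give f for this trial. The benchmark's upper quartile of 2.9 months would suggest about 0.75. Dabigatran up to the 90-day TEE might shift DAT later and lower f, but no figure supports a particular value. If half of the cleared thrombi recurred by 1 year, the n = 262 figures for f = 0.10, 0.25 and 0.50 would fall to 4%, 6% and 13-14%.

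**Why the net direction is open.** The benchmark divides by implanted devices, and the share imaged is not given. If 10% or 20% were never imaged (assumed), the rate per imaged device would be 82 / (2118 × 0.9) = 4.3% or 82 / (2118 × 0.8) = 4.8%. With that rate as b, the two effects cancel at f = (1 - 0.049 / (b + 0.01)) / s, which is about 0.08 or 0.17-0.18. Below that the net lean is against non-inferiority; above it, toward.

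**Power if 2.5% was meant as a 1-year rate.** The cumulative rate is then 0.025 / (1 - f × s). With s = 0.895 it is 2.75% at f = 0.10 and 3.2% at f = 0.25. By the same normal (Wald) method as reproduces 262, power for a cumulative endpoint is about 69% or 46% at n = 262, and 37% or 24% at n = 100.

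**The case against.** DAT present at 1 year, months after dabigatran stops, may be exactly what the sponsor wants to measure; section 1 and the Endpoints section both use that wording. On that view the endpoint is right and the benchmark is wrong. This stands, and the fix offers that route. It does not remove the mismatch, because 3.9% is still not a 1-year prevalence.

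The early thrombi are also not hidden. The section 3 objective would report them in a 3-month rate, section 2 sends TEE images for core-lab confirmation, and the Schedule of Study Procedures has a column for DAT visits. That is right, so a reader who infers that the data are lost goes too far. But the 3-month rate is not a listed endpoint, and nothing says how it combines with the 1-year rate.

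The probabilities rest on an assumed f and an assumed test, and the larger ones belong to an expansion that depends on funding. That also stands: they show sensitivity and do not forecast.

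A reader might infer that the trial is certainly biased toward non-inferiority against 3.9%. The documents do not support this, because the benchmark's imaging completeness and horizon are not given. Nor do they support treating a count through 1 year as fully like-for-like. The trial schedules no imaging between the procedure and 90 days, while the benchmark's median diagnosis was at 1.5 months.

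**Conclusion.** The concern holds as a mismatch of definitions. As written, the plan tests a prevalence at 1 year against an overall incidence, and no section makes a cleared 90-day thrombus a primary event. That one component leans toward non-inferiority. Its size depends on f: at the bound, the pass chance at n = 262 moves from 2.6% to 5% if f is 0.10, and to 43-49% if f is 0.50. At the committed n = 100 it moves from 4% to 6% and 24-27%. These figures assume the exact rule, treatment of every 90-day thrombus, 89.5-95% clearance and no recurrence. The sample size of 262 and the 46% pilot power are arithmetically correct, but they apply only to whichever kind of rate the 2.5% was meant to be. This should be fixed before analysis, and before any decision to expand.

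**What to change.** 1. **Endpoint.** Define the primary endpoint as any DAT confirmed by central review (echo lab for TEE, chest radiology for CT angiography) on any image after the procedure day through the 1-year visit, counted once per subject even if it resolves. Report thrombus seen at implant separately. List DAT present at 90 days and DAT present at 1 year as secondary endpoints. Align the objective in section 3 and the sample-size text.
2. **Alternative.** If DAT present at 1 year is intended, keep that endpoint, replace 3.9% with a matching 1-year rate, and restate sample size and power.
3. **Denominator.** Use one that does not depend on outcome, for example all implanted subjects with at least one follow-up image, with a sensitivity analysis for subjects lacking the 1-year image.
4. **Assumed rate.** State that the 2.5% is cumulative. If it was a 1-year rate, restate power for the cumulative endpoint as shown above.

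**Cost.** This is mainly wording, since the 90-day and 1-year images are already planned. Repeat images are discretionary, and section 2 mentions central reading of selected images, so the plan should say that every follow-up image bearing on DAT is read centrally. N stays at 262 only if 2.5% is already cumulative. Otherwise the same Wald method needs about 356 (f = 0.10) or 684 (f = 0.25) for 80% power. The reported DAT rate will be somewhat higher. Thrombi that form and clear before the 90-day image stay missed, so the cumulative count is closer to the benchmark but not identical to it.

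Separately, the 1-year imaging window is ±4 weeks in section 2 and ±14 days in the Schedule of Study Procedures; the two must be reconciled.

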### **Statistical Methods/Calculations:**

Statistical sample size calculation to establish comparable DAT rate with the prescribed regimen:

Available data for background on DAT;

Overall incidence of DAT was 3.9% (82 DAT for 2118 implanted devices)

Lempereur et al. Meta-Analysis [ref 19]: 30 studies describing DAT events were included in the analysis. The overall incidence of DAT was 3.9% (82 DAT for 2118 implanted devices). The median time from procedure to diagnosis of DAT was 1.5 months (IQR: 0-2.9). Most cases were diagnosed with transesophageal echocardiogram (TEE). The treatment consisted of low molecular weight heparin (LMWH) in 45.5% of cases, and oral anticoagulation (OAC) or other treatment modalities in 54.5%. Complete thrombus resolution was achieved in 95.0% of cases (100% with LMWH and 89.5% with OAC). Treatment duration varied greatly with a median treatment duration of 45 days (IQR: 14-

135). Clinical events related to DAT consisted of neurologic events namely two transient ischemic attacks (2.4%) and four ischemic strokes (4.9%).

Saw et al [ref 7]. 339 analyzable TEE in follow up. Patients' mean age was  $74.4 \pm 7.5$  years, and 67.3% were men. The mean CHADS2 score was  $2.7 \pm 1.3$ , the mean CHA2DS2-VASc score was  $4.3 \pm 1.5$ , and the mean HAS-BLED score was  $3.0 \pm 1.2$ . Peri-procedural major adverse events occurred in 2.4%. Median clinical follow-up duration was 355 days (range 179 to 622 days). Follow-up transesophageal echocardiography was performed after a median of 134 days (range 88 to 227 days). Device-associated thrombus was observed in 3.2% Independent predictors of device-associated thrombus were smoking (odds ratio: 5.79;  $p = 0.017$ ) and female sex (odds ratio: 4.22;  $p = 0.027$ ).

Kaneko et al. [ref 20] 78 patients (50 males,  $72 \pm 8$  years, average CHA2DS2-VASc score of  $4.3 + 1.8$ ) who had undergone WATCHMAN implantation. WATCHMAN was successfully implanted in all patients and four (5%) developed DRT. Patients with DRT were more often female (75 vs. 34%,  $p = 0.094$ ). CHA2DS2-VASc score was higher for patients with DRT ( $6.3 \pm 2.5$  vs.  $4.2 \pm 1.7$ ,  $p = 0.022$ ). Chronic kidney disease (100% vs. 43%,  $p = 0.024$ ) and deep implantation of the device, which was defined as implant position below the LAA ostial plane (75 vs. 24%,  $p = 0.026$ ), were more common in patients with DRT. HAS-BLED score ( $4.5 \pm 1.0$  vs.  $3.5 \pm 1.1$ ,  $p = 0.074$ ) was higher and oral anticoagulants (50 vs. 84%,  $p = 0.086$ ) were less commonly prescribed for patients with DRT. Multivariable logistic regression analysis showed that higher CHA2DS2-VASc score ( $p = 0.022$ , OR 2.8) and deep implantation ( $p = 0.032$ , OR 24.7) were associated with DRT. These results suggest the possible role of CHA2DS2-VASc scores and implantation depth in the development of DRT after percutaneous LAA closure using the WATCHMAN device.

With a single arm non-inferiority trial design to show the absolute rate of DAT is less than the control rate of 3.9% by a non-inferiority margin of 1% having a power 80% to detect a 1.4% difference at 0.05 level of significance, we would need 262 total subjects enrolled and reaching imaging endpoint evaluation. The initial study will begin with pilot to 100 subjects (with 46% power) with an option to expand if additional funding source is obtained.

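### The non-inferiority bound is worded as 2.9% but the sample size implies 4.9%; with limits holding about 5% error, power is 28% at 100 subjects and 52–67% at 262, not the stated 46% and 80%

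*Combined protocol and SAP*

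**What the plan says.** Statistical Methods/Calculations describes the design and its size in one sentence. It opens "With a single arm non-inferiority trial design" and gives the aim as "to show the absolute rate of DAT is less than the control rate of 3.9% by a non-inferiority margin of 1" per cent, "having a power 80% to detect a 1.4% difference at 0.05 level of significance", and concludes "we would need 262 total subjects enrolled and reaching imaging endpoint evaluation". It then adds: "The initial study will begin with pilot to 100 subjects (with 46% power".

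Section 2 (Study design) repeats the figures for the optional expansion, with no direction for the margin: "80% power to detect a 1.4% difference with the non-inferiority margin 1% in absolute rate of DAT (control rate 3.9" per cent.

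Section 3, in the paragraph on drug supply and study size after the exclusion criteria, gives another objective. "With either the 100-subject pilot study, or optional expanded single arm study (262 patients) the objective is to establish" a DAT (device-associated thrombus) "rate at 3 months and 1 year within 1.5% or less deviation from published DAT rates at 3.9" per cent.

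Nowhere does the plan print the bound as a single number, the assumed true rate, whether 0.05 is one- or two-sided, or the test or confidence limit to be used.

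**The concern.** The study has no control arm. The non-inferiority conclusion therefore rests on two things: the fixed bound, and the upper confidence limit compared with it. Both are open.

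- **Bound.** The sentence describes a rate lower than 3.9% by 1 point, which is a superiority-type claim against 2.9%. The non-inferiority label points to 3.9% + 1% = 4.9%.
- **Limit.** At a true rate of 2.5% about 2.5 events are expected in 100 subjects and 6.5 in 262. Common limits then disagree on which counts pass. In an unblinded single-arm study the choice should not be open once the count is known.
- **Power.** If the stated power rests on an approximation that does not hold 5% error at these counts, both sizes look more informative than they are. The 80% figure is also what a funder of the expansion would read.
- **Second criterion.** The 1.5% objective applies to either size but is not related to the 1% margin.

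**Working it through.** **Inputs.** Printed: control rate 3.9%, margin 1%, difference to detect 1.4%, level 0.05, power 80%, N = 262, pilot N = 100 with 46% power. Inferred: bound p0 = 3.9% + 1% = 4.9%; true rate p1 = 3.9% − 1.4% = 2.5%; one-sided 0.05.

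**1. Reproducing the plan's figures.** Normal approximation with the variance at the true rate (Wald):

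- n = (z0.95 + z0.80)² × p1(1 − p1) / (p0 − p1)² = (1.645 + 0.842)² × 0.025 × 0.975 / 0.024² = 261.6, so 262.
- Power = Φ[(p0 − p1)√n / √(p1(1 − p1)) − 1.645]. At 100: Φ(1.537 − 1.645) = 45.7%. At 262: Φ(2.488 − 1.645) = 80.0%.

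Both stated figures are recovered. The other single-arm readings tried are not compatible with them:

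| Bound | True rate | Variant | N for 80% | Power at 100 |
|---|---|---|---|---|
| 4.9% | 2.5% | two-sided 0.05 | 333 | 33.6% |
| 4.9% | 2.5% | variance at the bound | 501 | 29.7% |
| 4.9% | 2.5% | null and alternative variances | 411 | 23.1% |
| 3.9% | 2.5% | one-sided Wald | 769 | 22.7% |
| 2.9% | 2.5% | one-sided Wald | 9,419 | 8.2% |
| 2.9% | 1.5% | one-sided Wald | 467 | 31.1% |

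**2. What each upper limit delivers.** Success means that the one-sided 95% upper limit is below 4.9%. Power is the binomial probability of a passing count at 2.5%; error is the same probability at 4.9%.

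| N | Limit | Passes at | Power | One-sided error |
|---|---|---|---|---|
| 100 | Exact (Clopper-Pearson) | ≤1 | 28.3% | 4.0% |
| 100 | Wilson | ≤1 | 28.3% | 4.0% |
| 100 | Wald | ≤2 | 54.2% | 12.7% |
| 262 | Exact | ≤6 | 51.8% | 2.6% |
| 262 | Wilson | ≤7 | 66.6% | 5.4% |
| 262 | Wald | ≤8 | 78.8% | 10.2% |

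With 1 event in 100 the upper limits are 4.66% (exact) and 4.36% (Wilson). The probability of exactly 2 events in 100 at 2.5% is 25.9%. That is the count on which Wald disagrees with the other two.

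**3. Why a fixed event count is not a safe rule.** With 94 evaluable subjects, 1 event gives an upper limit of 4.95% exact (fails) and 4.63% Wilson (passes). Exact then requires 0 events, with power 0.975^94 = 9.3%.

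**4. The 1.5% objective.** Read as a condition on the observed rate, it means 2.4% to 5.4%: 3–5 events of 100, or 7–14 of 262. At 100 no such count passes under any of the three limits. At 262 the overlap is none for exact, 7 for Wilson, and 7–8 for Wald. Read as 95% precision, the half-width 1.96 × √(0.039 × 0.961 / n) is 3.8 points at 100 and 2.3 at 262, so neither size reaches 1.5.

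**The case against.** **The 2.9% reading is strained.** The non-inferiority label makes 4.9% recoverable. That is so, and this part is a drafting fault. It still needs correcting, because the sentence as written and its own sample size cannot both stand.

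**The origin of 262 is inferred.** No formula is printed. True, but one set of assumptions matches both stated figures and none of the alternatives tried matches them.

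**A Wald planning formula does not commit the study to a Wald analysis.** This is the strongest objection. Inflated error and overstated power are alternative harms. With a Wald analysis, power is about as stated or better (54% and 79%) but error is 13% and 10%. With exact or Wilson, error is about 5% or less and power falls. The stated power and the stated 0.05 level do not hold together under any of the three limits.

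**The 52% is partly an accident of 262.** Exact power moves in steps as N changes. This stands as a caution on the low end, as does Wilson's error of 5.4%, slightly above nominal.

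**It is a pilot with power already disclosed as below 50%, and the expansion depends on funding.** That limits the harm. But the plan attaches a power figure and a comparative objective to the pilot, and 80% to the expansion.

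**The 3.9% may not correspond to a 1-year imaging rate.** This is a separate question and does not affect the point here.

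**Conclusion.** The concern holds. The aim is worded as a 2.9% bound, while the sample size and pilot power rest on an unprinted 4.9% bound. At a 4.9% bound, a true rate of 2.5% and one-sided error of about 5%, power is 28% at 100 subjects rather than 46%, and 52% (exact) or 67% (Wilson) at 262 rather than 80%. The unnamed limit alone would decide a pilot with 2 events, a 26% chance at that true rate.

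The 262 is not an arithmetic error; the weakness is the approximation behind it. The conclusion assumes that 4.9%, 2.5% and one-sided 0.05 were intended, and that all 100 or 262 subjects have evaluable 1-year imaging; with fewer, the power figures shift. The conflict with the 1.5% objective is conditional on reading it as the observed rate. This should be fixed before data are seen.

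**What to change.** In section 2 and Statistical Methods/Calculations:

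- State H0: 1-year DAT rate ≥ 4.9% (3.9% + 1%) against H1: < 4.9%, one-sided alpha 0.05, with an assumed true rate of 2.5%. Reword the aim as a rate not higher than 3.9% by more than 1 point.
- Name one upper limit now. Exact is the conservative choice; Wilson is an acceptable alternative.
- Define success as that one-sided 95% upper limit, computed on subjects with evaluable 1-year imaging, falling below 4.9%. Do not use a fixed event count.
- Replace 46% and 80% with the power of the chosen limit: about 28% and 52% for exact, or about 28% and 67% for Wilson. Note that these assume 100 and 262 evaluable subjects.

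In section 3, say whether the 1.5% refers to the observed rate, a ceiling or precision, and how it relates to the 1% margin. Otherwise label it descriptive at 3 months and 1 year and not a success criterion.

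The cost is wording and a less favourable stated power, with no added subjects, visits or data. If the sponsor wants the expansion to keep 80% power, that is a separate sizing decision: an exact test at error ≤5% first reaches 80% at 394 evaluable subjects and holds it for every N from 443.

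### The 3.9% historical rate is an estimate (82/2118) but is used as a known constant, so the stated 80% and 46% power apply to a fixed 4.9% threshold and not to the comparison with a historical control

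*Combined protocol and SAP*

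**What the plan says.** Section 2 (Study design) describes a single-arm study in which "Comparison will be made to historical controls based on published one year DAT rates" from named trials and registries. It offers an optional expansion to a non-inferiority design "with the non-inferiority margin 1% in absolute rate of DAT (control rate 3.9"%).

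Statistical Methods/Calculations gives the source of that rate: "Overall incidence of DAT was 3.9% (82 DAT for 2118 implanted devices"). This is a meta-analysis in which "30 studies describing DAT events were included in the analysis". The same section then states the objective, that "the absolute rate of DAT is less than the control rate of 3.9% by a non-inferiority margin of 1" percentage point. The design is to have 80% power for a true advantage of 1.4 points, tested "at 0.05 level of significance". It arrives at 262 subjects reaching the imaging endpoint, and 46% power for the initial 100-subject pilot.

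The documents give no interval for the 3.9%, no variance term for it, and no named test or confidence limit for the comparison.

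**The concern.** Non-inferiority to a control rate is a statement about the difference between two rates. Here both are estimated: the trial rate from 100 or 262 subjects, the control rate from 82 events. If the calculation and the later analysis carry only the trial arm's variance, the interval for the difference is too narrow and the power for that comparison is overstated.

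The control rate's uncertainty is not small on the scale that matters. Its exact 95% interval reaches about 0.8 points below and 0.9 points above the estimate, against a margin of 1 point. The other rates quoted in the protocol also differ: 3.2% (Amplatzer Cardiac Plug), 3.7% at one year (EWOLUTION) and 4/78 = 5.1% (a Watchman series, printed as 5%).

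At stake are the power on which an expansion would be funded, and whether a result near the boundary counts as success.

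**Working it through.** **Inputs.** From Statistical Methods/Calculations: control rate 3.9% (82/2118), margin 1 point, assumed advantage 1.4 points, level 0.05 (sidedness not stated), n = 262 and 100. The assumed trial rate is therefore 3.9% − 1.4% = 2.5%. The boundary is 3.9% + 1% = 4.9%, so the distance to it is 2.4 points.

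**1. Reproducing the plan's figures.** One-sample normal formula, one-sided 0.05, variance at 2.5%, control rate fixed:

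- n = 0.025 × 0.975 × (1.645 + 0.842)² / 0.024² = 261.6, so 262.
- Power at 262: SE = √(0.025 × 0.975/262) = 0.00965; Φ(0.024/0.00965 − 1.645) = 80.0%.
- Power at 100: SE = 0.01561; Φ(0.024/0.01561 − 1.645) = 45.7%, stated as 46%.

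Other readings tried do not give 262: two-sided 0.05 gives 333, variance under the null 411, a boundary of 3.9% gives 769, and a boundary of 2.9% gives 9,419. The plan's figures therefore carry no variance for the control rate.

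**2. Uncertainty of the control rate.** 82/2118 = 3.87%; exact 95% CI 3.09% to 4.78%. SE = √(0.039 × 0.961/2118) = 0.00421.

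**3. Same approximation with that variance added.**

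- At 262: SE = √(0.00965² + 0.00421²) = 0.01052; Φ(0.024/0.01052 − 1.645) = 73.8%.
- At 100: SE = √(0.01561² + 0.00421²) = 0.01617; Φ(0.024/0.01617 − 1.645) = 43.6%.
- Setting power to 80% and solving for n gives 323 under this approximation.

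Between-study variation is not reported. If it inflated the control variance by 1.5, 2 or 3 (an assumption), power at 262 would be about 71%, 68% or 63%.

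**4. If the fixed-rate test is kept and the control rate is uncertain.**

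- Type I error at 262: the SE at 4.9% is √(0.049 × 0.951/262) = 0.01334. Φ(−1.645 × 0.01334/√(0.01334² + 0.00421²)) = 5.8% in place of 5%. At 100 it is 5.3%.
- Power at 262, averaged over the control's error: Φ((0.024 − 1.645 × 0.00965)/0.01052) = 78%.

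**5. Decision rules.** For each method, this is the largest DAT count that passes a one-sided 95% criterion. Power is the binomial probability of that count or fewer at a true rate of 2.5%, with the historical count held at 82.

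| Method | n = 262 | n = 100 |
|---|---|---|
| One-sample Wald limit, 3.9% fixed | ≤ 8 | ≤ 2 |
| Two-sample Wald limit against 82/2118 | ≤ 7, power 66.6% | ≤ 2, power 54.2% |
| Newcombe limit against 82/2118 | ≤ 6, power 51.8% | ≤ 1, power 28.3% |
| Exact one-sample test against 4.9% | ≤ 6, power 51.8% | ≤ 1, power 28.3% |

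At 262, eight events pass the fixed-rate Wald limit (upper limit for the difference 0.90 points) and fail the two-sample Wald limit (1.06 points). The Wald figure of 54% at 100 is not a gain: the same rule of two or fewer has probability 12.7% when the true rate is 4.9%, so it does not hold the 5% level.

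**The case against.** The best defence is that a fixed benchmark is a common convention in single-arm trials, and that 80% is the correct normal-approximation power for a test against 4.9%. This stands. A reader might infer that the true power of the planned test is 74%; the documents do not support that, because 74% belongs to a different comparison. If the fixed-rate test is kept, the cost of an uncertain control rate is a type I error of about 5.8% and power of about 78%. What the defence does not cover is the plan's language: it speaks of historical controls, a control rate and a non-inferiority margin, and nowhere calls 4.9% a performance goal.

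Second, the 262-subject stage depends on extra funding. The study to be run first is the pilot, already declared at 46%, where the change is about 2 points and the Wald decision is the same either way. This also stands.

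Third, the normal approximation is the larger source of optimism. An exact one-sample test with 3.9% fixed has the same cut-offs as Newcombe at both sizes. This stands, and it means that 74%, 44% and 323 cannot be attached to a Newcombe limit: at 323 its power is 70.9% (9 or fewer DAT).

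Finally, one could argue that a true control rate of 3.1% would turn 4.9% into a 1.8-point margin. That is only one side: a true rate of 4.8% would leave 0.1 point. The interval shows imprecision, not a bias towards leniency.

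**Conclusion.** The concern holds in a limited form. The plan describes non-inferiority to a historical control rate but calculates power for a test against a fixed number. For the comparison it describes, its own approximation gives about 74% at 262 (stated 80%) and 44% at 100 (stated 46%). These are best cases, since only the binomial error of the pooled 82/2118 is counted. They rest on a true rate of 2.5%, a one-sided 0.05 level (inferred because it reproduces 262) and the normal approximation.

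The material loss concerns the optional expansion. It would be too strong to say that the stated power is miscalculated or that the pilot is compromised: the figures reproduce, and the pilot barely changes. The choice of analysis should still be settled beforehand, because at 262 a count of seven or eight events passes or fails according to the method, and the plan names none. The section on dosing and drug supply applies the comparison with published rates to both sizes, so the pilot needs the specification too.

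**What to change.** Choose one of the following, and write it into Statistical Methods/Calculations before outcome data are seen.

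(a) **Compare with the historical estimate.** Base the conclusion on a named one-sided 95% upper limit for the difference between the trial rate and 82/2118, against +1 point, and state the power of that method. At a true rate of 2.5% with the historical count held at 82, Newcombe has about 52% at 262 and 28% at 100. Two-sample Wald has about 67% and 54%, with the caution above about its error rate at 100. Do not quote 74%, 44% or 323 alongside Newcombe. State that between-study variation is not included, and reconcile the 30-study pool behind 3.9% with the one-year trial and registry rates that section 2 names as the comparator.

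(b) **Use a performance goal.** Declare 4.9% a fixed goal and justify it, name the one-sample test, and state its power (about 52% at 262 and 28% at 100 for an exact test). Limit the conclusion to meeting the goal, without claiming non-inferiority to a historical control rate.

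Either option costs a few sentences and a less favourable power figure. The count 82/2118 is already in the plan. If the sponsor wants 80% power under the chosen method, the expansion would have to be larger than 262.
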